9.2 Follow-up Information

Recurrent episodes, complications, or progression of the initial event must be reported as follow-up to the original episode, regardless of when the event occurs. This report must be submitted within the same timelines immediately, without undue delay, but under no circumstances later than within 24 hours of the Investigator receiving the follow-up information (Note: if more stringent, local regulations regarding reporting timelines prevail). Any event that is considered completely unrelated to a previously reported one should be reported separately as a new event.

Follow-up information is sent to the same contact person to whom the initial information was sent, stating, where an AE report form is used, that this is a follow-up to the previously reported event and providing the date of the original report. If known, the information missing from the

initial report should be completed. The follow-up information should describe whether the event has resolved or continues, if and how it was treated, whether the patients continued or withdrew from study participation.

In case an SAE is not previously documented in the product information (EU SmPC or local equivalent), a Novartis Patient Safety associate may urgently require further information from the treating physician or other involved health care professional for Health Authority reporting.

In case an adverse event is considered to be of particular interest, a Novartis Patient Safety associate may seek additional information concerning the event. Corresponding questionnaires will then be provided by Novartis Patient Safety to the treating physician or other involved health care professional on a case-by-case basis.

12.1 Safety Questionnaire

Patient ID: _____

Date of Visit _____

Since the patient's last visit, has s/he experienced:

Ocular Event	No	Yes*, Right Eye (OD)	Yes*, Left Eye (OS)	Yes*, Both Eyes (OU)	Start Date	Ongoing/ End Date
Increased Intraocular Pressure						
Retinal Tear						
Macular Disorders						
• Macular Hole						
• Foveal Dehiscence						
• Maculopathy (e.g., epiretinal membrane, macular pucker)						
• Foveal thinning						
• Loss of foveal function						
Chorioretinal atrophy (e.g. injection site atrophy/treatment emergent progressive atrophy)						
Cataract						
Intraocular Inflammation and/or Infection Related to the Procedure						
Retinal Detachment						
Host Immune Response (Ocular)						
Lack of Efficacy						
Decline in Efficacy over Time						
Other ocular event, specify						

Event	No	Yes*	Start Date	Ongoing/ End Date
New or exacerbated neoplastic event, specify				
Third Party Transmission				
Host Immune Response (Non-ocular)				
New or exacerbated hematologic event, specify				
New or exacerbated neurologic event, specify				

***NOTE: If YES to any of the above, the event(s) MUST be reported as an Adverse Event or Serious Adverse Event and documented in eCRFs**

***NOTE: If yes to any of the above, please provide a narrative of the event(s), including relevant information (e.g., presenting signs or symptoms, relevant associated medical or ocular conditions, concomitant medications, tests performed to assess the event and results, treatment given for the event, etc).**

Event:
 
Narrative:

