Main protocol author(s)	[REDACTED], MD, [REDACTED] [REDACTED], PhD, [REDACTED] [REDACTED], PhD, [REDACTED] [REDACTED], PhD, [REDACTED] [REDACTED], MD, [REDACTED] [REDACTED], PhD, [REDACTED] Novartis Pharma AG, CH-4002 Basel, Switzerland
Principal investigator (PI)	[name]. med [REDACTED], DPhil [REDACTED] Germany
MAH contact person	[REDACTED], [REDACTED] Novartis Pharma AG, CH-4002 Basel, Switzerland

2 Abstract

Title

A Post-Authorization, Multicenter, Multinational, Longitudinal, Observational Safety Registry Study for Patients Treated with Voretigene Neparvovec

Version and date

v02, 11 March 2022

Name and affiliation of main author

[REDACTED]

Rationale and background

Voretigene neparvovec is a gene therapy developed to restore functional vision in adult and paediatric patients with confirmed biallelic *RPE65* mutation-associated retinal dystrophy. It was approved in the United States and European Union (EU) under the brand name Luxturna®. Inherited retinal dystrophy caused by biallelic *RPE65* mutations is a rare genetic condition. Mutations in the *RPE65* gene are associated with several clinical manifestations including nyctalopia, decreased visual field and decreased visual acuity. The individuals carrying these mutations exhibit vision loss that substantially limits major life activities, often during childhood or adolescence, and ultimately progresses to total blindness. Voretigene neparvovec uses a non-pathogenic recombinant adeno-associated virus vector serotype 2 (AAV2) to deliver cDNA encoding RPE65 protein to target cells in the retina, allowing for restoration of the visual cycle. Voretigene neparvovec is a one-time treatment. It is administered by subretinal injection in a dose of 1.5×10^{11} vector genomes in each eye separately, in a total volume of 0.3 mL.

Gene therapies, like voretigene neparvovec, are a novel class of therapy containing genetically modified organisms (GMO). Post authorisation follow-up of patients administered with gene therapy medicinal products is of interest due to limited data availability and is a post-approval requirement in the EU, agreed as part of the Risk Management Plan.

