Registration in the EU PAS register	Aug 2019

* Study progress reports will be provided annually in within the PSUR. A standalone study report will be provided if a PSUR is not due for submission.

3 Amendments and updates

Table 3-1 Study protocol amendments and updates

Numbers	Date	Section of study protocol	Amendment or update	Reason
v02	11 Mar 2022	Section 1, Table 1-1	Updates	Update sponsor contacts
		Section 5	Amendment	Added risk of vision loss due to progressive chorioretinal atrophy
		Section 7.2 Other Variables	Amendment	Inclusion and clarification of new PRO questionnaires,
		Section 7.3 Table 7-1	Updates	Added ocular characteristics and PRO collection to Table 7-1
		Section 7.6	Amendment Update	Added retinal atrophy sub-group analysis Updated FAS definition
		Section 9.1 & 9.2	Update	Updated AE reporting instructions
		Section 12.1	Amendment	Added Chorioretinal atrophy (e.g. injection site atrophy/treatment emergent progressive atrophy) to list of AESIs (Safety Questionnaire)
		Section 12.2	Amendment	Modified VFQ-25 Questionnaire Clarified completion instructions
		[REDACTED]	[REDACTED]	[REDACTED]
		[REDACTED]	[REDACTED]	[REDACTED]
		Section 12.5	Update	Relocation of BIC (previously was Annex 3)
		Section 12.6	Update	Relocation of ENCePP annex (previously was Annex 4)

4 Milestones

Table 4-1 Planned dates of study milestones

Study Active	Dec 2019
End of data collection	Dec 2029
Study progress reports*	Annually starting April 2020
Final report of study results	June 2030
Registration in the EU PAS register	Aug 2019

* Study progress reports will be provided annually within the PSUR. A standalone study report will be provided if a PSUR is not due for submission.

5 Rationale and background

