Voretigene neparvovec uses a non-pathogenic adeno-associated virus vector serotype 2 (AAV2) to deliver the *RPE65* genetic material to target cells in the retina.

Voretigene neparvovec is a one-time treatment. It is administered in a dose of 1.5×10^{11} vector genomes (vg) to each eye, delivered in a total subretinal volume of 0.3 mL. Prior to voretigene neparvovec administration, biallelic *RPE65* mutations must be confirmed by genetic testing in a certified laboratory, and patients must have viable retinal cells. Please refer to the locally approved product information for full product and prescribing information.

Important identified risks of voretigene neparvovec identified from the clinical development program include increased intraocular pressure, retinal tear, macular disorders (e.g., macular hole, foveal dehiscence, maculopathy [epiretinal membrane, macular pucker], foveal thinning or loss of foveal function), cataract, intraocular inflammation and/or infection related to the procedure and retinal detachment. Important potential risks for voretigene neparvovec include tumorigenicity, host immune response, and third-party transmission. Vision loss due to progressive chorioretinal atrophy is added as an important potential risk based on post-marketing experience.

This medicinal product contains genetically modified organisms (GMOs) i.e. viral vector. Based on the characteristics of voretigene neparvovec, the intended use after placing it on the market and the receiving environment, the inherent risk of third-party transmission associated with voretigene neparvovec are considered to be very low.

In clinical studies of voretigene neparvovec, only low levels and transient shedding of infective virus from treated individuals were detected. Additionally, any potential consequence of transmission of voretigene neparvovec is negligible due to the non-pathogenic nature of the

parental virus. Voretigene neparvovec is indicated for an ultra-rare disease, and will only be distributed through a limited number of treatment centers, where qualified staff (i.e. vitreoretinal surgeons and pharmacists) have participated in the mandatory educational program about use of the product. The manufacture, supply, and traceability of voretigene neparvovec is tightly controlled and monitored in accordance with pharmaceutical legislation.

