A patient will be considered potentially lost to follow-up if they do not return to the study site for the annual follow-up visits and no information can be obtained via telephone contact or other sources. The site is encouraged to make every effort (phone, email, certified mail) and document those efforts to regain contact to resume data collection. A patient cannot be considered as lost to follow-up until the time point of their scheduled End of Study visit has passed.

Variables

The safety profile of voretigene neparvovec, administered to patients who enroll in this study, should be evaluated based on the examination of general demographic and safety variables, including specific clinical measures.

Pre-treatment and Baseline characteristics

- Demographics (e.g. age, gender, race, ethnicity, and country of residence)
- Medical and surgical history (including prior gene and cell therapy)
- Ocular characteristics (including information on viable cells and ophthalmic exam results)
- Genetic diagnosis related to the inherited retinal dystrophy
- Clinical diagnoses related to the inherited retinal dystrophy
- Concomitant medications and procedures
- PRO and caregiver questionnaires

Voretigene neparvovec administration information

- Surgical center location
- Date of injection(s) (right eye, left eye)
- Lot number and volume administered (right eye, left eye)
- Details of perioperative corticosteroids use
- Surgical details including number and location of retinotomies (right eye, left eye)

Safety Variables

- The following events are designated as AESIs and will be queried through the standardized safety questionnaire ([Section 12.1](#)) and entered into the AE CRF:
 - Ocular AEs
 - Lack of efficacy and/or decline in efficacy over time*
 - Third-party transmission
 - Host immune response
 - Development or exacerbation of oncologic, hematologic, neurologic, or auto-immune diseases
- ***Note:** Signs and symptoms resulting from “lack of efficacy” or “decline of efficacy over time” or “failure of expected pharmacological action” should be provided in the AE or SAE description.
- Follow-up information on reported chorioretinal atrophy
- Any other AEs and SAEs
- Information on pregnancy occurrence, outcomes, and lactation (from patients and female partners of patient)
- Ophthalmic examination results for VA, VF, FST, and OCT:

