7.4 Study size

This study is intended to collect long-term safety follow-up information and the sample size estimate is not based on statistical measures. Every effort will be made to enroll all patients treated with voretigene neparovec, and it is expected that a minimum of 40 adult or pediatric patients can be enrolled over a five-year enrollment period.

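### Chorioretinal atrophy became a named questionnaire item only with version 02 and is asked about only since the last visit, so earlier atrophy in version 01 patients may be under-recorded

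*Protocol*

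**What the plan says.** - **The risk.** Section 5 states: "Vision loss due to progressive chorioretinal atrophy is added as an important potential risk based on post-marketing experience".
- **When the prompt arrived.** The row for Section 12.1 in the amendment table (Table 3-1) reads "Added Chorioretinal atrophy (e.g. injection site atrophy/treatment emergent progressive atrophy) to list of AESIs (Safety Questionnaire". The Abstract gives the version as "v02, 11 March 2022", and Table 4-1 gives "Study Active Dec 2019".
- **What the form asks.** In Section 12.1 the ocular rows, including "Chorioretinal atrophy (e.g. injection site atrophy/treatment emergent progressive atrophy", follow a lead-in that limits the question to the period since the patient's "last visit, has s/he experienced". The current form also has a catch-all row for other ocular events, a start-date column and an ongoing/end-date column.
- **What else is planned for atrophy.** The safety variables in Section 7.2 list "Follow-up information on reported chorioretinal atrophy". That follows up known cases; it does not search for unrecorded ones.
- **Retrospective capture.** Sections 7.2 and 9.1 require it for patients treated before enrollment, from dosing to registry entry.
- **Exempt events.** Section 9.1 does not require reporting of expected fundus changes that fit the underlying disease and come without a change in visual function.
- **Use of the data.** Section 7.6.2 tabulates adverse events cumulatively and/or annually. The annual tables are meant to show any rising or falling trend in reported events.

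**The concern.** The way atrophy is sought changes partway through the study, for the one risk that was added from post-marketing experience. A patient enrolled under version 01 was not specifically asked about atrophy until version 02 reached the site. Answered literally, the new row then covers only the interval since the previous visit. The retrospective rule does not close the gap, because it ends at registry entry. Between version 01 enrollment and the last visit before version 02, no passage provides a prompted look-back. The protocol does give patients separate instructions by protocol version for the questionnaires (Table 7-1, Section 12.2), but not for atrophy.

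Two readings of the final data are at stake. Cumulative incidence of atrophy could be too low. The annual tables could also show a rise that comes from better ascertainment and not from more disease. An analysis plan can label the two periods, but it cannot recover events that were not recorded.

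**Working it through.** The protocol gives no figure for this point, and its study size is not statistically derived, so there is nothing to reproduce. The following is an illustration.

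**Inputs from the protocol**
- Study active December 2019 (Table 4-1); version 02 dated 11 March 2022 (Abstract).
- Section 7.4: "a minimum of 40 adult or pediatric patients can be enrolled over a five-year enrollment period". Hence 40 patients over 60 months.
- Follow-up of five years after treatment (Section 7.2).

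**Assumptions**
- Entry time u is uniform over 0 to 60 months, and treatment takes place at enrollment.
- Sites switch on the version date.
- The true rate of new atrophy is constant, and follow-up is complete.
- s is unprompted capture as a fraction of prompted capture. The documents do not give s, so it runs from 0 to 1.

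**Step 1: time under version 01.** From 31 December 2019 to 11 March 2022 is 801 days, and from 1 December 2019 it is 831 days. Divided by 30.4375, the switch month A is 26.3 to 27.3.

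**Step 2: patients affected.** A/60 = 43.8% to 45.5%, and 40 × A/60 = 17.5 to 18.2, about 18 patients.

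**Step 3: unprompted share of each follow-up year.** For year k this is the mean over u of (A − u − 12(k − 1))/12, limited to the range 0 to 1.
- Year 1: (A − 6)/60 = 0.338 to 0.355.
- Year 2: (A − 18)/60 = 0.138 to 0.155.
- Year 3: (A − 24)²/(24 × 60) = 0.004 to 0.008.
- Years 4 and 5: 0.

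Averaged over five years, about 10% of planned follow-up is unprompted.

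**Step 4: apparent trend.** Apparent rate divided by true rate in year k is 1 − share × (1 − s). Year 5 is fully prompted, so the Year 5 to Year 1 ratio is 1/(1 − share₁ × (1 − s)).

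| s | Year 5 / Year 1 |
|---|---|
| 1 | 1.00 |
| 0.75 | 1.09 to 1.10 |
| 0.5 | 1.20 to 1.22 |
| 0.25 | 1.34 to 1.36 |
| 0 | 1.51 to 1.55 |

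**Step 5: cumulative count.** Under a constant rate the shortfall is about 0.10 × (1 − s): 5% at s = 0.5 and 10% at s = 0. If all atrophy arose in Year 1, it would be share₁ × (1 − s), at most about a third.

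**Step 6: sensitivity to the switch.**
- If sites adopted version 02 6 to 12 months late, the ratio is about 1.3 to 1.4 at s = 0.5 and about 1.8 to 2.25 at s = 0.
- In the other direction, the first version 02 form reaches back to the previous visit. If visits fell only on anniversaries of treatment, the Year 1 share would be (A − 12)/60 = 0.24 to 0.26, and the ratio at s = 0 would be about 1.3.
- Patients treated well before a version 01 enrollment could have longer unprompted time than modelled.

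**The case against.** The questionnaire is not the only route. Ocular adverse events as a class are of special interest, so atrophy judged an adverse event was reportable without its own row. All adverse events must be recorded, and patients are also asked about any other events at each visit. Events may be found by examination or other assessments. The recommended schedule includes OCT at baseline and Years 1 to 5, subject to routine care. Atrophy is a structural finding, so capture need not depend on what the patient volunteers. If it is still present at the first version 02 visit, the start-date column allows the earlier onset to be entered. The trend tables are optional and descriptive, and Section 7.8 acknowledges information bias in general terms.

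Most of this stands. A reader might infer that earlier atrophy in version 01 patients was certainly lost and that a false trend must follow. The documents do not support that: the routes above were open, and at s = 1 there is no artefact. The version 01 form is not shown, so whether it had the catch-all row cannot be checked. Nor can it be checked whether version 01 carried the fundus-appearance exemption, since version 02 updated Section 9.1. Instructions sent to sites with version 02 are not visible either.

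The objection does not show that unprompted capture equals prompted capture. Section 7.2 supplies the question list to standardize safety collection, while Section 9.1 otherwise seeks events by non-directive questioning. If the exemption applied under version 01, it could have discouraged recording of atrophy without functional change. Reportable is not the same as asked about.

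**Conclusion.** The point holds as possible differential ascertainment, not as demonstrated loss. Atrophy in version 01 patients that arose before their last pre-version-02 visit was reportable but not specifically prompted, and the protocol contains no later look-back for it. Cumulative incidence could be understated, and the annual tables could show an artefactual increase.

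The size is unknown because it turns on s. Under the stated assumptions about 18 of 40 patients entered under version 01 and about a third of Year 1 follow-up was unprompted. The Year 5 to Year 1 ratio under a constant true rate lies between 1.0 and about 1.5. Late adoption of version 02 would raise the upper end, and widely spaced visits would lower it. These figures describe time without a named prompt; they are not counts of missed events.

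The look-back is worth specifying in the protocol because it concerns data collection. How the tables are split can be left to the statistical analysis plan, which is not at hand and is not faulted here.

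**What to change.** Add to Section 12.1 that, at the first visit under version 02, each patient enrolled under version 01 is asked the atrophy row once as *at any time since treatment*. The site also checks OCT and ophthalmic records already on file and enters the earliest date on which atrophy is seen, for each eye. If back-capture is complete and dated correctly, the artefact in the working disappears (s = 1, ratio 1.00).

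When annual trends are reported, read atrophy with the change in ascertainment in view, for example by prompted and unprompted period, with details in the statistical analysis plan.

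The cost is one instruction and a one-time chart check at sites, with no new examination. Some retrospective onset dates will be approximate.

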7.6.2 Voretigene neparvovec safety

Adverse events including the AESIs, SAEs, and pregnancy occurrence and outcome information (including information collected in the Novartis Global Safety database) will be summarized in annual progress reports and the final study report. All AEs and SAEs will be provided in patient data listings. Additional listings, summaries, and graphics may be generated, as appropriate.

Adverse events will be coded to system organ class (SOC) and preferred term (PT) using the Medical Dictionary for Regulatory Activities (MedDRA). The incidence (number and percentage of patients with an AE observed one or more times) and number of events for each AE will be presented for AEs and SAEs, and will be tabulated by SOC and PT, both overall and by severity level and relationship to treatment and/or surgical procedure, as appropriate. This will be performed both for the cumulative duration of follow-up through the analysis time point of interest and/or on an annual basis, the latter to assess the potential, if any, for increasing or decreasing trend in reported AEs. Safety results will be presented by age categories.

Administration of voretigene neparvovec includes the surgical procedures of pars plana vitrectomy followed by voretigene neparvovec injection via bleb formation in the subretinal space. AEs associated with the administration procedures include: increased intraocular pressure, retinal tear, retinal detachment, macular disorders, cataract, and intraocular inflammation and/or infection related to the procedure. A comparative analysis of these ocular AEs between treated patients and published literature data on pars plana vitrectomy will be included in the progress reports.

The incidence of these identified AEs will be summarized descriptively for this study.

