All AEs from all patients enrolled in the study must be collected and recorded in the study database, irrespective of seriousness or causal association. For patients who have been dosed prior to the enrollment in the registry, all the AEs from the time of dosing upto the time of entry to the registry should also be collected and recorded in the registry database.

The occurrence of AEs should be sought by non-directive questioning of the patient at each visit during the study. AEs may also be detected when they are volunteered by the patient during or between visits or through physical examination, laboratory test, or other assessments. Medical conditions/ diseases ongoing before starting treatment with a study drug are only considered AEs if they worsen after receiving the Novartis drug of interest.

All AEs must be recorded on the AE case report form (CRF) with the following information:

1. the severity grade (mild, moderate, severe)
2. the site (right eye, left eye, both eyes, or non-ocular)
3. its relationship to the voretigene neparvovec (vector and/or transgene), the subretinal injection procedure, the concomitant use of corticosteroids that are administered as part of the treatment, a combination of these procedures and products (suspected/not suspected)
4. its duration (start and end dates or if continuing at final exam)
5. whether it constitutes a SAE

In addition, all reports of the following **special scenarios**, whether or not associated with AEs, are also collected and reported in the same manner as AEs:

- Drug-drug or drug-food interaction
- Drug use during lactation
- Lack of efficacy

- Overdose
- Intentional drug abuse and misuse
- Medication errors including drug maladministration
- Dispensing or prescribing errors
- Drug dependence or addiction
- Withdrawal reaction/ syndrome or rebound symptoms
- Unexpected beneficial effect
- Treatment non-compliance (with clinical symptoms)

A standardized safety questionnaire ([Section 12.1](#)) will be used, in conjunction with clinical observations and ophthalmic examination results, to solicit **Adverse events of special interest (AESI)** information. At each visit the patient should be specifically questioned on each of these AESIs. The AESI will be captured on the AE case report form (CRF).

The following events are designated AESIs:

- Ocular AEs
- Lack of efficacy and/or decline in efficacy over time
- Third-party transmission
- Host immune response

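### The named-risk figure for intraocular inflammation/infection has procedural causation built into its definition, so its incidence and the vitrectomy comparison rest on a site attribution that the registry cannot check

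*Protocol*

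**What the plan says.** The condition appears in three places in the protocol.

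- **12.1, Safety Questionnaire.** The row is "Intraocular Inflammation and/or Infection Related to the Procedure". Raised pressure, retinal tear, the macular disorders, cataract and retinal detachment are listed with no cause attached. The form also has a row for ocular host immune response and a row "Other ocular event, specify". A note adds: "If YES to any of the above, the event(s) MUST be reported as an Adverse Event or Serious Adverse Event".
- **7.6.2, Voretigene neparvovec safety.** The list of events associated with administration ends with "cataract, and intraocular inflammation and/or infection related to the procedure". The section promises a descriptive incidence of the listed events and a comparison with the published vitrectomy literature in the progress reports.
- **Section 5.** The important identified risks include "intraocular inflammation and/or infection related to the procedure and retinal detachment".

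Separately, 9.1 requires the adverse event form to record, for every event, "its relationship to the voretigene neparvovec (vector and/or transgene), the subretinal injection procedure, the concomitant use of corticosteroids", or a combination, as suspected or not suspected. Section 9.1 also requires all adverse events to be collected whatever their cause. Section 7.6.2 tabulates them by MedDRA class and term, both overall and by relationship.

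**The concern.** For five of the six event groups in the 7.6.2 list, the event is a finding: a tear, a cataract, a raised pressure. For the sixth, it is a finding plus a causal judgement. Section 7.6.2 itself describes administration as vitrectomy followed by subretinal injection, and 7.8 acknowledges that there is no control group. The documents give sites no rule for telling procedural inflammation from vector-related inflammation, and the study has no means of verifying the choice.

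At stake is the reading of one named risk. As a count of all intraocular inflammation, the 7.6.2 figure can only be too low. As a count of truly procedural inflammation, it can err either way. The literature comparison is affected most. Any excess over vitrectomy alone is where a vector contribution would show, and attribution can remove that excess before the comparison is made. The figure may also differ between sites for reasons of opinion, although 7.2 introduces the questionnaire to standardise safety collection.

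**Working it through.** The protocol states no rate, power or precision for this risk, so there is no figure to reproduce. The check compares the texts and adds one labelled illustration.

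**Step 1. Is the condition needed to obtain attribution?** No. The relationship item in 9.1 already records it for every event. With the condition also in the event's name, attribution is decided twice, and the two answers need not agree.

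**Step 2. Follow one finding through the form.** Take vitritis some weeks after surgery.

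| Site's view | Row in 12.1, read literally | In the 7.6.2 named-risk figure? | In the overall MedDRA table? |
|---|---|---|---|
| Procedure | Inflammation/infection | Yes | Yes |
| Vector or immune response | Host immune response (ocular), or other ocular event | Not as the category is worded | Yes |
| Unsure | Either, or more than one; no allocation rule is given | Depends on the site | Yes |

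The fourth column never changes; the third follows the site's opinion.

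**Step 3. Illustration.** Let k be the number of patients with any intraocular inflammation, s the share attributed to the procedure, and N = 40, the minimum enrolment expected in 7.4.

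- All-cause incidence = k / N
- Named-risk incidence = k × s / N
- Relative understatement = 1 − s

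Both k and s are assumptions. Patients are counted, following the incidence definition in 7.6.2. Exact (Clopper-Pearson) 95% intervals are in brackets.

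| k | All causes | s = 75% | s = 50% | s = 25% |
|---|---|---|---|---|
| 4 | 4/40 = 10.0% (2.8 to 23.7) | 3/40 = 7.5% (1.6 to 20.4) | 2/40 = 5.0% (0.6 to 16.9) | 1/40 = 2.5% (0.1 to 13.2) |
| 8 | 8/40 = 20.0% (9.1 to 35.6) | 6/40 = 15.0% (5.7 to 29.8) | 4/40 = 10.0% (2.8 to 23.7) | 2/40 = 5.0% (0.6 to 16.9) |

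The named figure moves in direct proportion to s. The intervals overlap widely at this size, so sampling error could hide the shift. It is a shift in definition, however, and enrolling more patients would not reduce it.

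**The case against.** The strongest reply is that nothing is lost. A reader might infer from the 12.1 row that inflammation is asked about and summarised only when procedural. The documents do not support that. All ocular events are of special interest, all adverse events are collected whatever the cause, non-directive questioning takes place at each visit, and two other rows of the form can take the episode. The overall tables by term are already planned. Nor does the registry omit vector-related inflammation: host immune response is a designated event of special interest and an important potential risk in section 5. All of this stands, and it limits the point to the named category.

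A reader might also infer that two ticks mean two adverse events. The note in 12.1 requires the event to be reported, not each tick. Section 9.2 treats recurrence and progression as follow-up to the original episode, and incidence in 7.6.2 counts a patient once per event. Double entry is possible, because no rule covers the overlap, but it is not prescribed.

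A third reply is that grouping MedDRA terms is work for the SAP, which is not shown, and that 7.6.2 need not be counted from questionnaire rows. This stands in part. A SAP could pool the terms for any cause, but it would then depart from the category as 7.6.2 words it, and it would not change the question on the form.

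Finally, the wording repeats the identified-risk term in section 5, and procedural inflammation set against vitrectomy is arguably like with like. That holds only if the attribution is reliable, which this design cannot show. The term itself can be kept as a sub-line.

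**Conclusion.** The point holds for three items: the wording of the 12.1 row, the identified-event incidence in 7.6.2 for this one risk, and its comparison with vitrectomy literature. Followed as written, these count a site attribution and can understate intraocular inflammation whenever episodes are assigned to the vector or to an immune response. The overall safety record is not compromised, since all-cause inflammation can be recovered from the coded terms.

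The size cannot be estimated from the protocol. The proportional loss is one minus the share attributed to the procedure, and that share is unknown; the percentages above only illustrate the mechanism. The conclusion assumes that sites and analysts apply the condition literally. It would weaken if the SAP already pools inflammation terms irrespective of cause for these outputs. The change is worth making because it is cheap and the attribution is already collected elsewhere.

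**What to change.** 1. **7.6.2.** Base the identified-event incidence and the literature comparison on all intraocular inflammation/infection, using pooled coded terms of any cause. Then split by the relationship item from 9.1. Keep the procedure-related subset as one line of that split, so that the identified-risk term in section 5 is still reported.
2. **12.1.** Reword the row to *Intraocular inflammation and/or infection (any cause)*. Instruct sites to enter one episode as one adverse event even when the ocular host immune response row also applies.

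The cost is one questionnaire row, one instruction and one table. Data already collected can be regrouped from the coded terms. There are two drawbacks. The form changes partway through the study, so annual summaries that span the change need a note that the question was widened. The headline inflammation figure will probably be somewhat higher, which the split by relationship will explain.
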